6.2. Design

Exploratory cohort study to investigate proof-of-principle with an established reference standard (Level 2b)

6.3. Setting

Tertiary referral centre

6.4. Participants

Patients with dysphagia referred to videofluoroscopy clinic at Sheffield Teaching Hospitals NHS FT.

6.5. Sample size

The aim of the current work is not to establish diagnostic accuracy of the equipment array, but rather to develop the hardware and processing algorithms for use in a future larger clinical trial.

Based on experience from similar projects, a sample size of 20 - 45 has been chosen for Part 2 of the study, with an intention to recruit the 3 patient groups described above, aiming for up to 5 - 15 in each group but with the understanding that targets will be subject to referral patterns within the study timescale.

We will not know which groups patients will fall into before testing, and so consecutive cases will be approached and consented for the trial. After recording from the device and analysis of the videofluoroscopy examination, patients will be allocated to one of the three groups. Data collection will continue until all either: a) each group has recruited 15 participants or b) recruitment time for the study is ended and data recorded from extra cases in already completed groups will still be entered into the analysis.

Age and sex matching will not be used, as is standard practice in this early stage of proof-of-principle research.

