aspiration, following initial videofluoroscopy as part of their usual clinical care.

Patients requiring follow up videofluoroscopy (either to check for deterioration or progress made in response to swallow therapy) will be sent a letter inviting them to their follow up appointment and explaining that they have the opportunity to participate in a research study on a voluntary basis. The letter will contain a patient information sheet explaining the study, and what participation will involve. Patients who express an interest in participating in the study they will be booked a double-length appointment to allow sufficient time for any delay that research participation may involve.

At their appointment the patient will be met by a research nurse and a study technician. The nurse will explain the study again, answer any questions and take written informed consent for study participation. The patient will have the option of declining to participate in the study with no effect on the planned videofluoroscopy study and ongoing clinical care.

The videofluoroscopy study will be performed in the standard manner, by two appropriately qualified Speech and Language Therapists and a Radiographer. In addition the aspiRATE equipment array will be attached by a study technician, in order to capture the additional data for the study so that it can be validated against the videofluoroscopy assessment.

Patients involved in Part 1 of the study will be asked to feedback on the design of the aspirate device, in particular the neck attachments. The radiographer performing the study will also be asked for feedback on the use of the device during videofluoroscopy, in particular to identify any hindrance to the acquisition or interpretation of images.

Once it has been confirmed that the equipment array can be easily applied, and does not interfere with standard videofluoroscopy, Part 2 of the study will be started. If it is found that the equipment array interferes with videofluoroscopy, progression to Part 2 will be halted until the issues are resolved.

Part 2. The primary aim of Part 2 of the trial is to collect data from a group of dysphagic patients using the proof-of-concept aspiRATE equipment array, allowing signal processing experts to develop the required multi-sensor analysis algorithms.

We aim to recruit up to 45 patients with dysphagia, according to referral rates within the timescale of the trial to the standard videofluoroscopy clinics within STH.

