6.7. Outcome measure(s)

As a proof-of-concept study the outcomes of interest are primarily qualitative: feasibility of the use of the equipment array, characteristics of acoustic signals from cases and controls, equipment safety and patient group feedback.

No statistical comparisons will be drawn between the case-control groups identified by the equipment array. A future clinical study will establish sensitivity and specificity of the equipment array as a device for the detection of aspiration, with reference to videofluoroscopy. This will be powered for the primary outcome of diagnostic accuracy.

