6.13. Project plan with timescale and clearly delineated milestones

The following internal review milestones have been set:

- Initial testing and assembly of experimental equipment array - underway
- Part 1: Completion of initial patient trials with VF once feasibility has been confirmed and obtained data is consistent with the aims of the project (i.e. able to analyse breath and additional sounds, and record pulse oximetry). Estimated 5 patients required. Target: March/April 2018
- Part 2: Completion of data collection from 20-45 patients seen in clinic. Target: April – October 2018
- Completion of a study. Target: December 2018

7. Statistical opinion

Although detailed statistical analysis is not predicted, given the early stage of this research, we will consult statistical advice from [name], Senior Lecturer in Statistics at Sheffield Hallam University in order to ensure that data analysis potential has been optimized. Initial discussions and sharing of the protocol have been completed with a view to seeking further guidance once (anonymized) data is available for analysis.

8. Project management

Internal management and review will be conducted by the project group at regular tele-conference or face-to-face meetings. [name], NIHR Devices for Dignity HTC Project Manager is part of the team and will provide expert project management overview. External review will be provided by [name] on behalf of the Cambridge Universities Health Partnership.

An application will be made for the study to be included in the NIHR Clinical Research Network (NIHR CRN) Portfolio, as it is part funded by NIHR via D4D and PRIDE.

As the equipment array is manufactured in-house in a health care establishment, and it is undergoing testing for proof-of-concept, it is not subject to the provisions of the Health Research Authority Medical Devices Regulations. In any future trial the Medicines & Healthcare products Regulatory Agency (MHRA) will be contacted, as commercialisation of a device may result from clinical data.

9. Expertise

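### Does the Part 2 stopping rule conflict with a sample size of up to 45?

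*Protocol*

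**What the plan says.** Section 6.1 (Part 2) states the size as an aim: "We aim to recruit up to 45 patients with dysphagia, according to referral rates within the timescale of the trial". Section 6.5 is firmer, "a sample size of 20 - 45 has been chosen for Part 2 of the study", but goes on to aim for up to 5 to 15 patients in each of three groups, "with the understanding that targets will be subject to referral patterns within the study timescale". Section 6.13 repeats the range as an internal review milestone: "Completion of data collection from 20-45 patients seen in clinic. Target: April – October 2018".

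Enrolment is consecutive, because "We will not know which groups patients will fall into before testing". Section 6.5 then gives the rule for ending recruitment: "Data collection will continue until all either: a) each group has recruited 15 participants or b) recruitment time for the study is ended". It adds that "data recorded from extra cases in already completed groups will still be entered into the analysis", so a group is not closed once it holds 15.

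Section 6.7 describes the outcomes as primarily qualitative and states: "No statistical comparisons will be drawn between the case-control groups identified by the equipment array". Section 6.5 says that the work is meant to develop hardware and algorithms, not to establish diagnostic accuracy.

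**The concern.** Read side by side, the three size statements make 45 a maximum, while limb (a) of the stopping rule makes it a minimum. Investigators cannot steer patients into groups, and surplus cases in full groups are kept. As soon as one group receives a 16th patient, limb (a) can no longer be met within 45. Apart from that limb, only the end of recruitment time stops enrolment.

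Suppose the 45th patient enrols with weeks left and one group below 15. Section 6.5 then says to continue, while sections 6.1 and 6.13 describe a study that is already at full size. Staff would have to decide whether to approach a 46th patient. Extra patients also have a cost: nurse time is budgeted for 6 months (section 15), and section 6.10 allows trial-only swallows with a small radiation exposure in a limited number of cases.

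**Working it through.** **Reproducing the stated figure.** Three groups (section 6.1) times 15 per group (section 6.5) gives 3 x 15 = 45, the upper figure. There is no power calculation to reproduce.

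**Chance that limb (a) is met at exactly 45.** This requires a 15/15/15 split, with probability 45!/(15!)^3 x (p1 p2 p3)^15. The protocol gives no group shares, so the shares below are assumptions. Equal shares maximise the product p1 p2 p3, so the first row is an upper bound.

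| Assumed shares (%) | P(limb (a) met at 45) | Mean total for limb (a), no time limit | Expected smallest group at 45 |
|---|---|---|---|
| equal thirds | 1.8% | 55.0 | 11.8 |
| 40/35/25 | 0.8% | 62.2 | 10.5 |
| 50/30/20 | 0.08% | 76.5 | 8.6 |
| 60/20/20 | 0.003% | 85.8 | 7.3 |

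The mean total is the sum over N of 1 - F(N), where F(N) is the multinomial probability that all three counts are at least 15 after N patients. The third column ignores limb (b), so it is not expected enrolment.

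**When the question arises.** It arises only if 45 is reached before recruitment time ends.

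- April to October 2018, taken as whole months, is 214 days, or 214/7 = 30.6 weeks. The threshold is 45/30.6 = 1.5 per week.
- With 26 weeks of funded nurse time (6 months, section 15), the threshold is 45/26 = 1.7 per week.
- The shorter window is plausible. The Part 1 target is March/April 2018 (section 6.13), and Part 2 starts only after Part 1 has confirmed compatibility (section 6.1).

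**Size of any excess over 45.** With S patients available, the expected total under the section 6.5 rule is the sum of 1 - F(N) for N = 0 to S - 1.

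- At 1 per week over 30.6 weeks, S = 30. At 1.5 per week, S = 45. The total equals S in both cases, so there is no conflict.
- At 2 per week over 26 weeks, S = 52. The expected total is 50.8 to 52.0 across the four mixes.
- At 2 per week over 30.6 weeks, S = 61. The expected total is 54.1 to 60.9.
- At 2.5 per week over 30.6 weeks, S = 76. The expected total is 55.0 to 74.1.

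**If recruitment stopped at 45 instead.** The expected smallest group, 7.3 to 11.8 in the table, lies inside the per-group aim of 5 to 15. A more uneven assumed mix of 60/30/10 gives 4.5, just under the lower end, but the aim is expressly subject to referral patterns.

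**Effect on results.** The groups are assigned after analysis of the videofluoroscopy examination. The rule therefore depends on group counts and the calendar, not on how well the device performs. Section 6.8 plans a 2x2 table with sensitivity and specificity. These are proportions within reference-standard categories, so stopping on group counts does not favour a good or a bad device result. Extra patients would only add data for algorithm development.

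**The case for a change.** The best argument for a change is that the ambiguity lies in the protocol's own recruitment rule and does not depend on any assumed mix. The upper size and the minimum for limb (a) are the same number, and the provision for extra cases makes limb (a) unreachable within 45 once any group overshoots. The phrase "a sample size of 20 - 45 has been chosen for Part 2 of the study" is firmer than an aim, and the proviso on referral patterns mainly explains a shortfall, not an excess. A single clause would tell staff whether to approach patient 46.

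The arithmetic stands, and so does the point that no sentence expressly makes 45 a cap or says that it may be exceeded. Three things weaken the case. First, the text gives a workable reading: 20 to 45 is a planning range, and section 6.5 holds the only instruction on when data collection ends, one that already foresees surplus cases. Second, the 98.2% chance (100% - 1.8%), at the least, that some group is short at 45 is conditional on reaching 45 early; it is not the probability of a problem. Third, a cap would not lower any promised group size, because 15 is the top of a per-group aim that starts at 5.

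**Conclusion.** The concern is factually right, but it is a gap in wording that the study team can fill sensibly by following section 6.5 as written. Limb (a) will almost never be met at 45 (at most 1.8%), so recruitment will in practice usually end either on time or somewhat above 45. Below about 1.5 enrolments per week the question does not arise. At 2 per week the expected total is roughly 51 to 61, depending on the window and the mix, and recruitment time bounds it in every case.

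Nothing the study reports depends on the choice. No power is claimed, outcomes are primarily qualitative, no between-group comparison is planned, and accuracy is left to a later trial. A clarifying clause would record which reading the sponsor meant, without improving the results or altering a conclusion. The totals and group sizes rest on assumed shares and enrolment rates that the protocol does not give. The minimum of 45 for limb (a) and the 1.8% upper bound hold for any fixed group shares.

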6.6. Recruitment: (see section 6.1 for recruitment procedures in context)

Part 1 clinical trial

Patient identification: by STH Speech and Language Therapy staff reviewing the medical notes of patients awaiting videofluoroscopy follow up appointments

Inclusion criteria: Dysphagia ± aspiration, age 18 and above

Exclusion criteria: Not competent for consent, previous neck surgery (not including thyroid surgery), cervical skin infection or defect, pregnant (or unknown pregnancy status).

Approach: By posted letter, with an enclosed trial patient information sheet

Recruitment: Through response to the letter

Consenting: On the day of testing, by a research nurse

Part 2 clinical trial

Patient identification: Patients attending a routine videofluoroscopy appointment at STH.

Inclusion and exclusion criteria: as above.

Approach: By posted letter, with an enclosed trial patient information sheet

Recruitment: On the day of testing, by a research nurse

Consenting: On the day of testing, by a research nurse

6.7. Outcome measure(s)

As a proof-of-concept study the outcomes of interest are primarily qualitative: feasibility of the use of the equipment array, characteristics of acoustic signals from cases and controls, equipment safety and patient group feedback.

No statistical comparisons will be drawn between the case-control groups identified by the equipment array. A future clinical study will establish sensitivity and specificity of the equipment array as a device for the detection of aspiration, with reference to videofluoroscopy. This will be powered for the primary outcome of diagnostic accuracy.

6.8. Analysis including statistical methods

[figure not shown]
Anonymized data (from both the equipment array and the videofluoroscopy) will be examined by the research team. Standard methods of analysis will be applied to acoustic recordings to assess the differences between those from aspirating and non-aspirating patients, and to compare these findings with the aspirating and non-aspirating videofluoroscopy data. An auditory processing algorithm that can be applied to future recordings will be developed.

Data from the device (index test) and videofluoroscopy (reference standard) will be used to populate a standard 2x2 table, allowing calculation of the device sensitivity and specificity. Receiver Operating Characteristic (ROC) curve analysis will allow refinement of the signal processing algorithm and interpretation thresholds, although as a screening test false positives will be considered preferable false negatives.

[figure not shown]
6.9. Intervention:

Patient Pathways

Part 1 Trial

Part 2 Trial

Flow chart indicating participant's involvement throughout the course of the study

6.10. Safety assessment:

The following issues have been considered as part of the risk assessment process of the new equipment array.

- Device obscures visualization of swallow on videofluoroscopy due to inadequate radiolucency – Videofluoroscopy assessments will be conducted by speech and language and radiography professionals, and initial testing (part 1 trial) includes built-in time to allow

the device to be adjusted or modified to improve videofluoroscopy views. In individual patients testing will be terminated early if inadequate views can be obtained for clinical use.

- Equipment prevents adequate patient positioning for videofluoroscopy – The attachment of the equipment attachment will be designed in conjunction with Speech and Language Therapists ensuring that it should not prevent the expected patient positioning. Initial PPI and the Part 1 trial are designed to allow refinement of the design if positioning proves problematic. In individual patients testing will be terminated early if positioning is inadequate for clinical use.
- Patient aspirates during videofluoroscopy – Aspiration is expected in some patients during videofluoroscopy and the risk should not be increased by use of the new equipment array. Most episodes of aspiration during videofluoroscopy have no sequelae. The equipment will be easy to remove and will not interfere with the provision of supportive treatment after aspiration in the unlikely event this is required.
- Radiation exposure – All participants in this study will already be undergoing videofluoroscopy for clinical reasons. In a limited number of cases, during the examination (which required multiple swallows to be performed) additional swallows may be requested to provide data for use only in the trial. The recording of any additional swallows would expose the patients to small amounts of ionizing radiation. This risk has been assessed by [name], Head of Radiology Physics and Radiation Protection Adviser at Sheffield Teaching Hospitals NHS FT.
- Electrical shock risk – Only the low voltage microphones and pulse oximetry probe will make contact with the patient. The equipment array will be assembled and checked by medical engineering professionals to meet EU medical device safety standards.
- Allergy to medical adhesives used to attach the microphones – standard echo cardiology sensors will be used with additional measures as per individual patient need
- Infection control risk. All research project equipment which would contact patients' skin will be for disposal single patient use. Research project equipment which will not be in contact with patients' skin and the usual videofluoroscopy equipment will be sanitized according to Sheffield Teaching Hospitals Infection Control guidance.
- The protocol has received scientific review from [name], Royal College of Speech and Language Therapy Advisor in Dysphagia (Manchester) and Clinical Lead in Dysphagia University Hospital South Manchester NHS Foundation Trust.

Adverse events will be discussed at pre-existing institutional audit sessions, and reported online using standard STH incident report forms. In addition regular meetings of the study steering committee (co-investigators and CUHP representative) will allow further discussion. If a concern arises regarding device safety recruitment will be suspended until the risk has been mitigated.

A serious adverse event (SAE) occurring to a participant will be reported to the REC giving favourable opinion to the study. An SAE will be reported if the Chief Investigator believes the event may be: 'related' (resulted from administration of any of the research procedures); and 'unexpected' (not listed in the protocol as an expected occurrence). Reports of related and unexpected SAEs will be submitted within 15 days of the Chief Investigator becoming aware of the event, using the NRES report of serious adverse event form.

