The most interesting line of research has been the analysis of lower airway (tracheal) sounds during swallows, with one group reporting an accuracy of 86% for the detection of swallows with silent aspiration⁷. This method aims to detect the end result of aspiration (food or liquid below the vocal cords), and so should have a higher specificity than is found with other techniques.

Pulse oximetry has also shown some potential as a measure of silent aspiration, but current consensus in the literature is that, while it has value as an adjunctive measure, it is not sufficiently reliable for use in isolation⁸.

The unique element to our work is a multi-channel approach using an array of microphones, and sophisticated processing of the audio and other sensor outputs. We will start by recording swallow and tracheal sounds via multiple microphones, in conjunction with pulse oximetry. Signal processing experts within the team will pick out characteristic signals associated with the normal swallow and episodes of aspiration. Through the development process we will narrow down the minimum set of sensors required to optimise test sensitivity and specificity. It may be that multiple measurements of the same type (sounds) or a mixture of measurement types (sounds and pulse oximetry) will give us the most information. We believe the microphone array and multi-channel analysis design can be superior in sensitivity and specificity when compared to existing reported techniques⁷.

PPI evaluation will be undertaken to explore the acceptability/tolerability of wearing the equipment array, and also the potential perceived benefits of access in the community to objective swallow safety assessment, particularly for groups previously excluded by cognitive or physical challenges. Sheffield Teaching Hospitals NHS FT has access to a database of patients and carers who have previous or ongoing experience of swallowing problems, and who have agreed to act as reviewers for studies. A focus group consisting of these individuals will be arranged by letter of invitation.

A robust prototype will be designed and manufactured collaboratively by Sheffield Teaching Hospitals NHS FT and Cambridge University, to incorporate the final set of sensors and analysis software. The aim is for this equipment array to be approved for research use in patients, and assessed in a proof of concept trial.

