6.1. Methodology

Preliminary testing / Public and patient involvement

The team has agreement to access a database held by Sheffield Teaching Hospitals NHS FT of individuals who have or have had dysphagia, and who have consented to support the development of research studies. This database will be used to identify potential invitees for a focus group discussion. Refreshments will be provided and travel arranged/travel costs reimbursed. We hope to form a group of 6-8 patients and carers to discuss:

- their experiences of current screening and diagnostic options
- an outline explanation of the aims of this project
- discussion of any perceived benefits/challenges to any potential trial participants
- opportunity to see and try the proposed aspiRATE equipment

A clinician known to database members (but not a member of the research team) will send out the initial invitation letter. She will also host the group along with one person from the research team. We aim for a relaxed and open discussion in order to gain valuable feedback on the important considerations for users in any testing, and specific comments on the proposed study design. The team will be open to suggestions regarding modifications that may make the trial more user-friendly. The equipment array will be fitted to volunteers from the user group at this event to gain feedback on comfort and acceptability.

Clinical trial

The trial can be considered in two parts:

- Part 1, which will focus on tolerability during videofluoroscopy and ensure that there is no adverse impact on the usual clinical care
- Part 2, where dedicated trial staff will collect data with the equipment array alongside standard clinical care.

Part 1. The primary aim of part 1 of the trial is to ensure that the equipment array can be used alongside videofluoroscopy in a manner that doesn't impede the clinical utility of the examination. It will allow technical and radiology staff to familiarize themselves with performing the study protocol, additional time will be allowed for each of these procedures, in order to reduce time pressure and members of the research team will be on hand for support. We envisage 3-5 patients should be a sufficient sample to complete this first phase.

Eligible patients will be identified by the Speech and Language Therapy team at Sheffield Teaching Hospitals NHS FT. These will be patients who are known to experience at least occasional

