We will aim to recruit consecutive patients in one of three cohorts

1. Dysphagia with no aspiration
2. Dysphagia with clinically detectable aspiration (coughing, wet voice)
3. Dysphagia with silent aspiration

Potential trial participants will again be identified by the Speech and Language Therapy team at Sheffield Teaching Hospitals NHS FT. Once again a letter inviting trial participation will be sent, with a patient information leaflet enclosed.

On attending the clinic, the patient will be met by a research nurse to ask if they are interested in finding out more about the study. The nurse will explain the study again, answer any questions and take written consent for study participation. A study technician will attach the equipment array prior to the videofluoroscopy assessment, and be present to assist the radiographer if needed. Acoustic recordings and pulse oximetry data will be collected during the videofluoroscopy examination with no change to the standard protocol. The patient will be asked for feedback and their involvement in the trial will finish at the end of the clinic appointment.

For the purpose of the study videofluoroscopy findings will be interpreted using the Rosenbek Penetration-Aspiration Scale¹⁸, and acoustic and pulse oximetry recordings from aspirating and non-aspirating swallows will be compared by signal processing experts to identify any characteristic

features in those where aspiration occurred.

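### Section 6.8 tunes the algorithm and thresholds by ROC and also calculates sensitivity and specificity, with only the 20-45 Part 2 patients to serve both; as written, the figures are apparent accuracy, biased upward

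*Protocol*

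**What the plan says.** Section 6.8 contains two steps. The first is tuning: "Receiver Operating Characteristic (ROC) curve analysis will allow refinement of the signal processing algorithm and interpretation thresholds". The second is scoring: with the array as index test and videofluoroscopy as reference standard, the paired data "will be used to populate a standard 2x2 table, allowing calculation of the device sensitivity and specificity". The section also says that false positives are to be preferred to false negatives.

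Section 6.1 gives the purpose of Part 2 as data collection, "allowing signal processing experts to develop the required multi-sensor analysis algorithms". Section 6.5 sets its size at 20-45, with up to 5-15 in each of three cohorts (no aspiration, clinically detectable aspiration, silent aspiration). The only other patient recordings come from Part 1, which concerns tolerability and compatibility with videofluoroscopy: "We envisage 3-5 patients should be a sufficient sample to complete this first phase".

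Features are also to be found by inspection. Section 5 says "Signal processing experts within the team will pick out characteristic signals associated with the normal swallow and episodes of aspiration", and section 6.1 says that "recordings from aspirating and non-aspirating swallows will be compared by signal processing experts".

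The protocol limits its own claims. Section 6.2 describes an "Exploratory cohort study to investigate proof-of-principle with an established reference standard", and section 6.5 says "The aim of the current work is not to establish diagnostic accuracy of the equipment array". Section 6.7 leaves sensitivity and specificity to a future powered study. Section 13 takes the device forward if it shows a degree of discrimination between aspirating and non-aspirating patients, without saying which estimate is meant.

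**The concern.** When a feature and a cut-point are chosen because they separate a set of patients well, the sensitivity and specificity counted in those same patients are too favourable on average. The smaller the sample and the more features tried, the larger the excess. With 20-45 patients and an open search over microphones, oximetry and signal features, both conditions are unfavourable.

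Two things are at stake. First, section 13 conditions further development on discrimination seen here, and same-data figures can suggest discrimination where there is none. Second, the optimism also falls on sensitivity, which section 6.8 most wants to protect. A cut-point that reaches a high sensitivity in the tuning patients will, on average, miss more aspirating patients among new ones.

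**Working it through.** **No figure of the plan to reproduce.** The 20-45 rests on experience from similar projects; no alpha, power or precision target is given. The upper end is 3 x 15 = 45. The lower end is not 3 x 5 = 15, but section 6.5 makes group sizes subject to referral patterns, so this is not an error.

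**Is there a second dataset?** Part 2 (20-45) is for development. Part 1 has 3-5 patients, whom section 6.1 describes as already known to aspirate at least at times, so they could say little about specificity. No hold-out set, resampling, or locking of the algorithm before the 2x2 table is described.

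**Size of the bias, by simulation.** Inputs from the protocol: Part 2 size and three cohorts. Assumptions not in the protocol:
- Cohorts 2 and 3 are the positives and cohorts are about equal, giving 30 vs 15 at N = 45 and 13 vs 7 at N = 20.
- There is one value per patient, with independent standard normal features.
- The best of 1, 5 or 20 candidate features is kept.
- The cut-point gives at least 90% same-data sensitivity (27/30 = 0.900; 12/13 = 0.923).

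Optimism = apparent value minus the expected value of the same rule in new patients.

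Pure noise (true AUC 0.50), 2,000 runs per setting, for 1 / 5 / 20 features:

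| | 30 vs 15 | 13 vs 7 |
|---|---|---|
| Mean apparent AUC | 0.574 / 0.644 / 0.697 | 0.611 / 0.717 / 0.793 |
| Apparent sensitivity | 0.900 | 0.923 |
| New-patient sensitivity | 0.856 / 0.832 / 0.813 | 0.836 / 0.790 / 0.752 |
| Apparent specificity | 0.174 / 0.244 / 0.306 | 0.212 / 0.342 / 0.458 |
| New-patient specificity | 0.144 / 0.168 / 0.187 | 0.164 / 0.210 / 0.248 |

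At 30 vs 15, sensitivity is overstated by 4 / 7 / 9 points and specificity by 3 / 8 / 12. At 13 vs 7 the excess is 9 / 13 / 17 and 5 / 13 / 21 points.

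One real feature (true AUC 0.80), 1,500 runs: new-patient sensitivity is 0.872 / 0.869 / 0.862 against 0.900 (3-4 points) and 0.858 / 0.828 / 0.798 against 0.923 (6-13 points). Specificity is barely biased here with a single feature.

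**A different tuning rule.** With the Youden cut-point and (sensitivity + specificity)/2 as the measure, noise gives 0.59 / 0.65 / 0.70 at 30 vs 15 and 0.63 / 0.72 / 0.78 at 13 vs 7, where the truth is 0.50. The bias was upward in all 30 scenarios tried, from about 7 to 31 points.

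**Does cross-validation by patient remove it?** On noise, sensitivity + specificity should be 1.00.
- Apparent, 20 features: 0.900 + 0.306 = 1.206 (30 vs 15); 0.923 + 0.458 = 1.381 (13 vs 7).
- 5-fold, with feature and threshold chosen in each training fold: 0.99-1.01. With 3 or 4 patients in the smaller group and that many folds: 0.99-1.02.
- Feature fixed on all data, only the threshold cross-validated, 20 features: 1.177 and 1.341. The share of optimism removed is (1.206 - 1.177)/0.206 = 14% and (1.381 - 1.341)/0.381 = 10%.

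The last case is the closest to experts choosing features after seeing every recording.

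**Precision.** Exact binomial 95% limits are the 2.5% point of Beta(x, n-x+1) and the 97.5% point of Beta(x+1, n-x): 24/30 = 80% (61-92%); 12/15 = 80% (52-96%); 10/13 = 77% (46-95%).

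**The case against.** The strongest reply is that accuracy is not an outcome of this study. Sections 6.2, 6.5 and 6.7 say so, section 7 plans further statistical advice once data are available, and the details of internal validation commonly sit in a SAP, which is not shown here. This limits the harm and the severity. It does not remove the point, because section 6.8 itself commits to both tuning and scoring, and the procedure as stated yields biased numbers. Advice sought after the recordings have been compared comes late for fixing the folds and the scoring rule.

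It is also fair that the size is not established. Feature counts, the 90% target and the cohort split are assumptions, and the results move widely with them.

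Four stronger readings are not supported:
- *That the protocol says the 2x2 table uses the tuning patients.* It does not say so; this is inferred from the absence of other data.
- *That these figures will set the sample size of the later trial.* Section 13 speaks only of building on the data collected.
- *That cross-validation would make the figures validated accuracy.* Where experts select features on the full data, most of the optimism may remain.
- *That the device defines the patient groups, as one phrase in section 6.7 suggests.* Section 6.5 allocates groups after the videofluoroscopy analysis and section 6.8 makes videofluoroscopy the reference standard. The phrase is a separate editorial slip and carries no weight here.

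**Conclusion.** The point holds as stated in the heading. Followed as written, section 6.8 produces apparent accuracy, biased upward on average. The direction follows from choosing and scoring the rule on the same patients. The size is illustrative: a device with no information would show a mean apparent AUC of about 0.57-0.70 at 30 vs 15 and 0.61-0.79 at 13 vs 7 when the best of 1-20 features is kept, and the excess in sensitivity is smaller when a real signal exists. The conclusion rests on the inference that Part 2 serves both steps. Severity is minor to moderate: the later powered trial is meant to settle accuracy, so the consequence is confined to how the exploratory figures, and the go-forward condition in section 13, are read.

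**What to change.** 1. **Section 6.8.** State one rule, fixed before scoring, that turns a patient's swallows into a single patient-level call. Estimate sensitivity and specificity by stratified 5-fold cross-validation by patient, with all swallows of a patient in one fold, and with algorithmic feature selection and threshold choice (keeping the stated preference for false positives) redone in each training fold. If the aspirating or non-aspirating group has fewer than 5 patients, use as many folds as that group has patients. Fill the 2x2 table from one prespecified random fold assignment, so that each patient has one call and the exact binomial 95% CI is defined. Describe that CI as approximate: in simulation its coverage was 86-98% for sensitivity and 91-98% for specificity. Show repeated partitions only as a sensitivity check. Label any same-data figure, including the AUC, as apparent, and all accuracy figures as exploratory.
2. **Also in 6.8.** State that features or sensors chosen by experts on the full data leave optimism, possibly most of it, that cross-validation does not remove. Report how many were tried.
3. **Section 13.** Read discrimination from the cross-validated figures with their CIs and this caveat, not from apparent figures, and do not present them as validated accuracy.

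As a separate editorial correction, section 6.7 should describe the groups in line with sections 6.5 and 6.8.

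**Cost.** Protocol wording and some computing time on stored recordings; no extra patients. The figures will be less favourable and the intervals wide. In the smallest samples sensitivity will be somewhat conservative: at 13 vs 7, cross-validated sensitivity was 4-7 points low and specificity 2-7 points high.
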